2.2.3. Nonclinical Safety

In the repeat dose toxicity studies in adult (up to 28 days) and neonatal/juvenile rats and dogs, the MTDs were defined by body weight loss and reduced food consumption accompanied by adverse clinical observation of varying severity. In dogs, there was dose-related incidence of emesis and liquid feces at ≥ 15 mg/kg/day. The key target organ for toxicity in adult animals was the hepatobiliary system, which included both degenerative and inflammatory changes in bile duct, in rats (≥ 60 mg/kg/day) and dogs (≥ 45 mg/kg/day). In dogs, the hepatobiliary findings correlated with elevated plasma levels of ALP, ALT, and GGT. In addition, the findings observed only in rats were in kidney (degeneration/regeneration of medullary tubules) at ≥ 120 mg/kg/day, lung (vascular degeneration/necrosis) at 240 mg/kg/day (non-tolerated dose), and trachea (epithelial degeneration and subepithelial inflammation [predominantly in females]) at 120 mg/kg/day in 14 and/or 28-day studies. In the 28-day dog repeat dose toxicity study, the NOAEL was 15 mg/kg/day corresponding to C_{max} of 729 ng/mL and AUC_{tau} of 9510 ng.h/mL. In the 28-day rat repeat dose toxicity study, the NOAEL was 60 mg/kg/day corresponding to C_{max} of 322 ng/mL and AUC_{tau} of 4725 ng.h/mL.

In the embryo-fetal toxicity studies in rat (GD6-17) and rabbit (GD6-18), there were no effects on pregnancy or embryo-fetal development. In rat, the NOAEL for maternal toxicity was 45 mg/kg/day based on the transient initial body weight loss followed by dose-related decreased body weight gain at ≥ 45 mg/kg/day. The NOAEL for embryo-fetal toxicity in rat was 60 mg/kg/day, corresponding to systemic maternal exposure (AUC_{24}) of 9830 ng.h/mL on Day 15 of gestation. In rabbit, maternal toxicity was limited to lower body weight gain and food intake at 45 mg/kg/day. The NOAEL for embryo-fetal development in rabbit was 45 mg/kg/day, corresponding to a systemic maternal exposure (AUC_{24}) of 220 ng.h/mL on Day 16 of gestation.

Further details of the nonclinical toxicology program are included in the IB.

2.2.4. Clinical Overview

Table 2. Completed PF-07923568 Studies

| Study Number (Status) | Study Type/Key Design Features | Study Population | Dose, Dosing Regimen | Formulation Used |
|---|---|---|---|------------------------|
| C5241001- previously REVC001 ^a (completed) | Phase 1, randomised, double-blind, placebo-controlled, safety, tolerability, PK, food-effect of single ascending dose (SAD) and multiple ascending dose (MAD) | Healthy participants | Dose range: 10 mg – 525 mg (SAD); 36 participants Dose range: 175 mg – 350 mg; BID (MAD), food effect; 24 participants | Liquid Formulation DIC |
| C5241002- previously REVC002 (completed) | Phase 2a, randomised, double-blind, placebo-controlled | Healthy participants inoculated with RSV CV | 200 mg or 350 mg BID for a total 10 doses; 66 participants | DIC |
| C5241004- previously REVC004 (completed) | Phase 1, adaptive, part-randomised, part open-label, drug interactions, safety and tolerability | Healthy participants | 200 mg; BID; 62 participants | DIC |
| C5241005- previously REVC005 (completed) | Phase 1, open-label, single-dose, PK, safety, and tolerability | Healthy participants | 200 mg, 4 single doses total; 9 participants 1 ×: DIC (fed) 1 ×: DPB (fed) 1 ×: DPB dispersed in H ₂ O (fed) 1 ×: DPB dispersed in H ₂ O (fasted) [wash-out: 3 days between each of the 4 dosing days] | DIC DPB |

a. A total of 8 participants received the liquid dosage formulation of PF-07923568 in a solution, at a concentration of 5 mg/mL, containing hydroxypropyl-β-cyclodextrin (HBP cyclodextrin), Lycasin, flavoring agent (strawberry) benzoic acid and water, and 68 subjects received DIC in the study.

Abbreviations: BID = twice-daily dosing; DIC = PF-07923568 drug in capsule; DPB = PF-07923568 dry powder blend; MAD = multiple ascending dose; PK = pharmacokinetic; RSV = respiratory syncytial virus; RSV CV = RSV challenge virus; SAD = single ascending dose.

A total of 201 adult healthy participants have received PF-07923568 in 4 completed clinical studies (C5241001, C5241002, C5241004, and C5241005) investigating the PK profile, effects of food on PK, effects of formulation on PK (C5241001, C5241005), DDIs (C5241004), and the efficacy in an RSV Viral Challenge Study (C5241002) at doses ranging

from 10 mg to 525 mg. In addition, as of 14 November 2022, 49 pediatric patients hospitalized due to RSV LRTI have been enrolled into the ongoing C5241003 study.

The administration of PF-07923568 was well tolerated at all doses, dosage forms, and dosing regimens tested. In the adult healthy participants treated to date, the occurrence of TEAEs considered related to PF-07923568 has been low. Most commonly reported treatment-related TEAEs were in the GI disorders SOC; nausea, diarrhea, and abdominal pain. These TEAEs have been mild to moderate in intensity and resolved without sequelae. Most events attributed to IMP involved the GI tract with nausea, diarrhea, and abdominal pain/discomfort/distension being the most common and occurring more commonly with the 350 mg dose of PF-07923568 than with the 200 mg PF-07923568 dose, where the number of participants reporting these events were lower and similar to those on placebo. In children, PF-07923568 is required to be suspended in a solution to enable oral administration, there has been evidence of poor tolerability when PF-07923568 was suspended in water as a single dose of 2.0 mg/kg in children aged 6-36 months, resulting in expulsion of the oral dose. Suspension in breast milk, formula milk, or saline appeared to improve the palatability, with all doses being successfully administered to children aged 1-36 months in study C5241003.

As of 22 November 2022, there have been no SAEs attributable to PF-07923568 and no deaths in the clinical studies.

In adults, under both fasting and fed conditions, PF-07923568 is slowly absorbed reaching maximum plasma concentrations (t_{max}) at 5-6 hours (hrs) with a relatively moderate clearance, resulting in a half-life of 7-10 hrs in healthy participants. Dosing to steady state resulted in steady state concentrations being reached after approximately 2 days of dosing resulting in 2-4 fold accumulation of exposure. AUC and C_{max} values increased in a greater than dose proportional manner across single and multiple dose studies. Following 5 days of dosing, the variability in PK parameters was high, with % CV ranging from 67.4-84% for C_{max} and 71.9-144% for AUC_{12} .

The effect of food on the single dose PK was assessed for the DIC formulation and DPB formulation dispersed in water. For the DIC the extent of systemic exposure to PF-07923568 (geometric mean AUC_{inf} under fed and fasted conditions) was 357 and 221 ng.h/mL, respectively, with the between-subject variability being lower under fed conditions (CV 64.1% compared with 198%). The ratio of fed/fasted was 218% (90% CI 94.2 - 502%) for C_{max} and 162% (90% CI 83.0 – 316%) for AUC_{0-inf} . It should be noted that the DIC fasted results from C5241001 were lower than typically seen in other studies with 200 mg administered under fasting conditions resulting in an artificially higher ratio of fed/fasted in this study. For the DPB dispersed in water the extent of systemic exposure to PF-07923568 (geometric mean AUC_{inf}) under fed and fasted conditions was 371 and 337 ng.h/mL, respectively, with the between-subject variability being slightly lower under fasted conditions (CV 49.0% compared with 61.6%). The ratio of fed/fasted was 107.7% (90% CI 78.0 – 148.8%) for C_{max} and 110.0% (90% CI 85.6 – 141.4%) for AUC_{inf} .

Clinical DDI Study C5241004 demonstrated that the disposition of PF-07923568 is expected to be affected by moderate to strong inhibitors and inducers of CYP3A4. Furthermore,

PF-07923568 was demonstrated to be a moderate inhibitor of CYP3A4, so dose adjustments for compounds that are sensitive substrates for CYP3A4 may need to be considered.

In an RSV challenge study, PF-07923568 treatment resulted in a statistically significant reduction in AUC of RSV viral load compared with placebo; 55.25% (p=0.007) and 63.05% (p=0.002) for the 200 mg and 350 mg PF-07923568 dose groups, respectively (dosed every 12 hrs [Q12H] for 5 days). Results for the AUC of total symptom score were consistent with the viral load AUC. Geometric mean AUCs of total symptom score were 195.56, 30.79, and 31.76 hrs for placebo, 200 mg PF-07923568 and 350 mg PF-07923568, respectively. The reduction in AUCs of total symptom score compared with placebo was statistically significant for both PF-07923568 treatment groups; p=0.009 (70.84%) and p=0.002 (74.42%), (Wilcoxon Rank-Sum test) for the 200 mg and 350 mg PF-07923568 dose groups, respectively.

More detailed information about results of clinical studies for PF-07923568 may be found in the IB.

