1.3. Schedule of Activities

The SoA table provides an overview of the protocol visits and procedures. Refer to the **STUDY ASSESSMENTS AND PROCEDURES** section of the protocol for detailed information on each procedure and assessment required for compliance with the protocol.

The investigator may schedule visits (unplanned visits) in addition to those listed in the SoA table, in order to conduct evaluations or assessments required to protect the well-being of the participant.

Table 1. Study Schedule of Activities

| Visit Identifier/Day [list of abbreviations in Appendix 11] | Screen ≤-28 to -2 | Day -1 | Day 1 | | | | | | | | | | | | Day 2 | Day 3 | Day 4 | Day 5 | Day 6 | ET | Follow-up ^a Day 29-36 | |
|--|-------------------------|----------------|----------------|---|---|---|---|---|----------------|---|----|----------------|----|----|-------|-------|-------|-------|-------|----|-------------------------------------|----|
| | | | 0 | 1 | 2 | 3 | 4 | 5 | 6 | 8 | 10 | 12 | 14 | 24 | | | | | | | -- | -- |
| Hours Post Dose | | -- | | | | | | | | | | | | | | | | | | | | |
| Informed consent & demography | x | | | | | | | | | | | | | | | | | | | | | |
| Outpatient visit | x | | | | | | | | | | | | | | | | | | | | | |
| Inpatient stay at CRU | | x | → | → | → | → | → | → | → | → | → | → | → | → | | → | → | → | x | | | |
| COVID-19 assessment ^b | | | | | | | | | | | | | | | | | | | | | | |
| Eligibility assessment | x | x | x | | | | | | | | | | | | | | | | | | | |
| Medical history | x | | | | | | | | | | | | | | | | | | | | | |
| Child-Pugh Classification scoring | x | | | | | | | | | | | | | | | | | | | | | |
| PE (height & weight at screening only) ^c | x | x | | | | | | | | | | | | | | | | x | x | | | |
| Breath alcohol & Urine drug test | x | x | | | | | | | | | | | | | | | | | | | | |
| Alcohol/tobacco & contraception use ^d | x | x | | | | | | | | | | | | | | | | x | x | x | x | |
| (Update) Prior/concomitant treatments | x | x | → | → | → | → | → | → | → | → | → | → | → | → | → | → | → | x | x | x | x | |
| Single, supine 12-lead ECG ^e | x | x | x ^e | | | | | | | | | | | | x | | | | x | x | | |
| Single, seated vital signs (BP, pulse rate) ^e | x | x | x ^e | | | | | | | | | | | | x | | | | x | x | | |
| AE monitoring (non-serious & SAEs) | x | → | → | → | → | → | → | → | → | → | → | → | → | → | → | → | → | x | x | x | x | |

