| Standard meals/optional snacks ^f | x ^f | x | | x | x | x | x | x | x | x | x | x | x | x | x | x | x | x | x | | | |
| Study intervention administration ^g | | x | | | | | | | | | | | | | | | | | | | | |
| Blood & Urine for clinical laboratory tests ^h | x | x ^j | | | | | | | | | | | | | | | | x | x | | | |
| Serology for FSH (all females), HIV, HBsAg, HCVAb/RNA | x | | | | | | | | | | | | | | | | | | | | | |
| Serum pregnancy test (all females) | x | | | | | | | | | | | | | | | | | | | | | |
| Urine pregnancy test (WOCBP only) ⁱ | | x | | | | | | | | | | | | | | | | x | x | | | |
| Blood for PK sampling for PF-07923568 and Blood:Plasma | | | x ^j | x | x | x | x | x | x ^k | x | x | x ^k | x | x | x | x | x | x | x | x | | |
| Retained Research Sample for Genetics (Prep D1) ^l | | | x ^j | | | | | | | | | | | | | | | | | | | |

Table 1. Study Schedule of Activities

| Visit Identifier/Day [list of abbreviations in Appendix 11] | Screen ≤-28 to -2 | Day -1 | Day 1 | | | | | | | | | | | | Day 2 | Day 3 | Day 4 | Day 5 | Day 6 | ET | Follow-up ^a | |
|---|-------------------------|-----------|----------------|---|---|---|---|---|---|---|----|----|----|----|-------|-------|-------|-------|-------|----|------------------------|--|
| | | | Day 1 | | | | | | | | | | | | | | | | | | Day 29-36 | |
| Hours Post Dose | | -- | 0 | 1 | 2 | 3 | 4 | 5 | 6 | 8 | 10 | 12 | 14 | 24 | 48 | 72 | 96 | 120 | -- | -- | -- | |
| Retained Research Sample for Biomarkers (Prep B2) ^m | | | x ^j | | | | | | | | | | | | | | | | | | | |

- a. Follow-up visit to be performed as telephone contact and must occur in the window of 28 to 35 days (ie, Day 29-36) from administration of study intervention. A clinic visit may be performed in place of telephone contact, if deemed necessary by the investigator, eg, for follow-up of abnormal laboratory tests and/or open AEs.
- b. Assessment of risk for, symptoms of or testing for COVID-19 may be performed at screening, admission to the CRU, and/or at other times during the study at investigator discretion and according to local site policies.
- c. Complete PE at screening; at all other time points limited PE, at investigator discretion (see [Section 8.3.1](#)).
- d. In confirmation of appropriate contraception use only.

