- e. If done around the time of a blood draw, ECG and vital sign assessments (BP and pulse rate) should be collected before the blood draw. ECG and vital signs on Day 1 at Time 0H must be done before collection of the pre-dose blood samples. If an IV catheter is utilized for blood sample collections, ECGs and vital sign assessments (BP and pulse rate) should be collected before insertion of the catheter.
- f. Meals/snacks to be served at clock times matching approximately 0H, 4H, 6H (optional snack), 10H, and 14H (optional snack) relative to dosing on Day 1, while inpatient. Meals/snacks on Day -1 must be timed such that there is at least an 8 hour fast prior to collection of the pre-dose PK sample on Day 1 (see [Section 5.3.2](#)).
- g. Dosing to occur with standard morning meal provided approximately 30 minutes prior to 0H, and meal completed approximately 10 minutes prior to dosing.
- h. Safety related laboratory tests collected on Day -1, **if performed** at investigator discretion, must be reviewed prior to dosing and must reflect the participant to be in stable medical condition.
- i. Test result must be reviewed and deemed acceptable (ie, negative) to continue participation in the study.
- j. Samples at 0H on Day 1 must be collected pre-dose.
- k. Whole blood aliquot (approximately 0.15 mL) will be collected from PK samples for in vivo blood:plasma ratio assessment.
- l. Prep D1 Retained Research Samples for Genetics: If not collected on the designated collection day, collect at the next available time point when biospecimens are being collected in conjunction with a participant visit.
- m. Prep B2 Retained Research Samples for Biomarkers: If not collected on the designated collection day, collect at the next available time point when biospecimens are being collected in conjunction with a participant visit.

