2.3.1. Risk Assessment

| Potential Risk of Clinical Significance | Summary of Data/Rationale for Risk | Mitigation Strategy |
|---|--|---|
| Study Intervention PF-07923568 | | |
| Hepatobiliary system effects | Degenerative and inflammatory changes in the bile duct of both rats (≥ 60 mg/kg/day) and dogs (≥ 45 mg/kg/day) in studies of up to 28 days, with elevated plasma levels of ALP, ALT, and GGT in dogs only. Evidence of recovery for all findings following a 14-day treatment-free period. | Standard monitoring including laboratory (ie, transaminases, ALP, GGT) and AE monitoring. |

| Potential Risk of Clinical Significance | Summary of Data/Rationale for Risk | Mitigation Strategy |
|---|---|---|
| Gastrointestinal effects | 
Transient dose-related incidence of emesis and liquid feces in dogs at doses ≥ 15 mg/kg/day in studies up to 28 days. Additionally, inflammation in the duodenum, gall bladder, and liver at 45 mg/kg/day noted in 28-day dog study.
 
In previous clinical studies sisunatovir has been associated with mild GI AEs in fasted state.
 | As this is an investigational agent, there is some risk that is mitigated by close observation of AEs, etc. Participants will be closely evaluated in an inpatient setting to monitor for GI AEs. If needed, palliative alleviating measures such as antiemetics may be provided. |
| Renal effects | Degeneration/regeneration of medullary tubules was noted in rats at ≥ 120 mg/kg/day in studies of up to 28 days; considered non-adverse based on lack of clinical pathology changes. | Standard monitoring including laboratory and AE monitoring. |
| Cardiovascular effects | 
Myocardial degeneration and necrosis were noted at 240 mg/kg/day (non-tolerated dose) in a 14-day rat study.
 
No similar effect in rats at 120 mg/kg/day in the 28-day study, or in dogs at any dose, for 14 or 28 days.
 
Phase 1 first-in-human (FIH) study (C5241001) showed no adverse clinically significant changes in safety laboratory parameters (including troponin), ECGs, and VS.
 | Monitoring will include VS, including heart rate and ECG assessments. |

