9.3.3.1. Electrocardiogram Analyses

Changes from baseline for the ECG parameters HR, QTcF, PR interval, and QRS complex will be summarized by treatment and time. The frequency of uncorrected QT values above 500 ms will be tabulated.

The number (%) of participants with maximum post-dose QTcF values and maximum increases from baseline in the following categories will be tabulated by treatment:

Safety QTcF Assessment

| Degree of Prolongation | Mild (ms) | Moderate (ms) | Severe (ms) |
|-------------------------------|------------------|----------------------|--------------------|
| Absolute value | >450-480 | >480-500 | >500 |
| Increase from baseline | | 30-60 | >60 |

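### No scheduled post-dose ECG or vital-sign set falls between 1 and 14 h, although t_max is 5-6 h, so the planned QTcF maxima do not cover peak exposure

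*Protocol*

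**What the plan says.** **Exposure profile.** Protocol 2.2.4 states that, fed or fasted, "PF-07923568 is slowly absorbed reaching maximum plasma concentrations" at 5-6 h, "resulting in a half-life of 7-10 hrs in healthy participants". No t_max or half-life is given for people with hepatic impairment.

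**Assessment times.** In Table 1 (Protocol 1.3) the rows for the single supine ECG and for "vital signs (BP, pulse rate") carry the same marks: screening, Day -1, Day 1 at 0 h, Day 2, Day 6 and early termination (ET). Footnote e makes the Day 1 set pre-dose: "ECG and vital signs on Day 1 at Time 0H must be done before collection of the pre-dose blood samples". PK blood is drawn at every nominal time on Day 1: 1, 2, 3, 4, 5, 6, 8, 10, 12 and 14 h.

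**What relies on these readings.**
- Protocol 9.3.3.1 counts participants by "maximum post-dose QTcF values and maximum increases from baseline in the following categories". This applies to QTcF. For BP, Protocol 9.3.3 plans only review, descriptive summary and a description of abnormalities.
- Protocol 8.3.3 starts repeat ECGs when a post-dose QTcF has risen by at least 60 ms and exceeds 450 ms, or when QT reaches 500 ms at a scheduled ECG.
- Protocol 2.3.1 gives as mitigation for cardiovascular effects: "Monitoring will include VS, including heart rate and ECG assessments".
- Protocol 3 makes ECG parameters and vital signs two of the four components of the secondary endpoint.

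**SAP.** Sections 6.6.3 and 6.6.4 say only that vital-sign and ECG data will be held in the database and supplied on request. Section 2.1 declares no change from the protocol's analysis.

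**The concern.** A table of maximum post-dose QTcF in which few participants cross a threshold is easily read as reassurance over the whole exposure range, including the peak. With this schedule, a completer's maximum is the larger of two scheduled readings, the first of which comes 18-19 h after t_max.

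This matters more here than in a study of healthy volunteers. Protocol 4.2 expects exposure to rise with impairment and notes that, for some compounds cleared in a similar way, the rise exceeds 2-fold in severe impairment. Protocol 2.2.4 reports greater than dose-proportional exposure and high variability. Groups 2-4 may enter with a screening QTcF of up to 470 ms, against 450 ms in Group 1 (Protocol 5.2.2 and 5.2.3). The secondary objective is safety and tolerability in exactly these groups, and the highest concentrations are the ones without a planned ECG or BP reading. The primary PK comparison is not affected.

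**Working it through.** The documents give no figure for exposure at the ECG times, so there is none to reproduce. The check has two parts.

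**1. Table 1 marks.** The ECG and vital-sign rows each have six marks. Three are before dosing (screening, Day -1, 0 h). One is an ET visit, which a completer does not have. That leaves Day 2 and Day 6. None of the ten post-dose times from 1 to 14 h is marked. In the text available for this review, the hours row and the visit row of Table 1 are one column out of step. Read against the visit row, the first post-dose mark is Day 2, which is 24 h. Read literally against the hours row it would be 48 h, further from the peak. Neither reading puts a mark between 1 and 14 h.

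**2. Concentration at those times as a share of Cmax.** Inputs from Protocol 2.2.4 are t_max 5-6 h and half-life 7-10 h. A doubled half-life (14-20 h, t_max unchanged) is an assumption, added to show sensitivity to impairment.

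Distance from the peak: 24 - 6 = 18 h to 24 - 5 = 19 h, which is 18/10 = 1.8 to 19/7 = 2.7 half-lives.

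- Method A, log-linear decline from the peak: share = 2^(-(t - t_max)/t_half). For example, 2^(-19/7) = 15.2% and 2^(-18/10) = 28.7%.
- Method B, one-compartment oral model: C(t) proportional to exp(-ke·t) - exp(-ka·t), with ke = ln 2 / t_half and ka solved from ln(ka/ke)/(ka - ke) = t_max. This allows for absorption continuing after t_max.

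| t_max, half-life (h) | ka (per h) | 24 h, A | 24 h, B | 120 h, A | 120 h, B |
|---|---|---|---|---|---|
| 5, 7 | 0.354 | 15.2% | 21.1% | 0.001% | 0.002% |
| 6, 7 | 0.260 | 16.8% | 26.6% | 0.001% | 0.002% |
| 5, 10 | 0.438 | 26.8% | 31.8% | 0.035% | 0.041% |
| 6, 10 | 0.329 | 28.7% | 36.3% | 0.037% | 0.047% |
| 5, 14 (assumed) | 0.520 | 39.0% | 43.1% | 0.34% | 0.37% |
| 6, 14 (assumed) | 0.396 | 41.0% | 46.9% | 0.35% | 0.40% |
| 5, 20 (assumed) | 0.607 | 51.8% | 54.9% | 1.9% | 2.0% |
| 6, 20 (assumed) | 0.469 | 53.6% | 57.9% | 1.9% | 2.1% |

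With the protocol's values, the 24 h set is at 15-36% of Cmax and the 120 h set below 0.05%. With the doubled half-life they are at about 39-58% and 0.3-2%.

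For scale only, and not as a proposed time: with the protocol's values, method B stays at about 90-100% of Cmax from 4 to 8 h. The finding does not depend on the exact t_max.

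**The case against.** **The schedule is a design choice and contradicts nothing.** A maximum post-dose value is naturally the largest of the values collected. Protocol 9.3.3.1 does not claim to capture peak exposure, 2.3.1 promises monitoring without stating times, and no objective concerns a concentration-QTc relation. This is fair as far as the wording goes. A reader might infer that the protocol asserts a peak measurement and then fails to make one; it does not assert that. What stands is that three safety provisions rely on readings that, with the plan followed exactly, are all scheduled well off the peak.

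**Other readings can fill the gap.** Protocol 8.3 allows unscheduled safety measurements and 8.3.2.1 allows extra or changed BP and pulse times. ET sets may fall at other times, and AEs are monitored throughout the stay. So it would be wrong to infer that no reading can ever occur near the peak. But unscheduled measurements respond to a perceived issue or need. They do not systematically detect a silent QTcF change.

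**The evidence of cardiac risk is thin.** Protocol 2.3.1 reports no clinically significant ECG or vital-sign changes in the first-in-human study, and a myocardial finding only in rats at a non-tolerated dose. This lowers the urgency. A reader might infer that the schedule hides a known QT effect or leaves participants unsafe; the documents show no such signal. They also do not turn a 24 h reading into one at peak.

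**The table may never be produced.** The SAP only databases these data. That weakens the prediction that a null table will be misread. But the SAP also declares no modification, so 9.3.3.1 still stands on paper and the two documents disagree.

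**t_max in impairment is unknown.** True, and it is a limit on the calculation. It does not by itself support having scheduled sets only at 24 h and 120 h.

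**Conclusion.** The point holds for scheduled readings in participants who complete the study. Their post-dose ECG and vital-sign sets are at 24 h and 120 h, when concentration is about 15-36% and below 0.05% of Cmax, or about 39-58% and 0.3-2% if impairment doubled the half-life. The QTcF categories in 9.3.3.1, the triggers in 8.3.3 and the mitigation in 2.3.1 therefore do not cover peak exposure, apart from any unscheduled or ET reading. BP and pulse have the same timing gap. A reader might extend the label of maximum post-dose result to BP as well, but the protocol uses it for QTcF only.

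This rests on t_max and half-life in healthy adults, on simple decline models, and on reading the first post-dose mark as Day 2. The doubled half-life is an assumption. The figures describe exposure, not effect: the documents give no relation between concentration and QTcF, so the size of any missed change cannot be stated. The point deserves action because correct labelling costs little and the population is the one in which higher exposure is expected.

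**What to change.** 1. The sponsor should reconcile the ECG and vital-sign times in Table 1 with the t_max in Protocol 2.2.4 and with 2.3.1, 8.3.3 and 9.3.3.1. Which times to use is the sponsor's decision.
2. If the times stay, Protocol 9.3.3.1 and the study report should label the QTcF results as the larger of the 24 h and 120 h scheduled readings, identify any unscheduled or ET readings separately, and state that the results do not support a conclusion at peak exposure.
3. SAP 6.6.3 and 6.6.4 should be aligned with Protocol 9.3.3 and 9.3.3.1. Either the SAP plans the summaries that the protocol describes, or SAP 2.1 records the departure.

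**Cost.** Items 2 and 3 need document changes and, if the summaries are kept, their programming. If the sponsor chose to move an existing set, there would be no extra visit, because participants are inpatients with PK draws throughout Day 1. The 24 h or 120 h reading might then be lost, and footnote e, which places ECGs and vital signs before insertion of any IV catheter, would need adjusting.
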